**Overview**

For Aim 5 80 (ages 25-65) Gold 0-2 subjects that are current smokers (defined by PFTs, questionnaires and interviews as discussed below) will be recruited. Participants will be equally distributed between males and females and will be representative of the national racial/ethnic populations. Subjects will be recruited using advertisements, email blasts, smoking cessation clinic and physician referrals. Participants that are enrolled into the study will have a total of 4 visits (baseline, 30 day, 60 day and 90 day) over 3-4 months. During the study visits, subject will have vitals, blood tests, urine sample, CT scans, pulmonary function tests, and complete questionnaires. Subjects will also participate in a smoking cessation program. Subjects will be contacted weekly, by phone, for smoking cessation follow up.

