**Schedule of Study Assessments and Procedures**

Activity	Consenting visit	Baseline visit	30 day visit	60 day visit	90 day visit
Written Informed Consent	X	X			
Pre-screen Inclusion/Exclusion form	X	X			
Human Subject Questionnaire		X			
St. George's Respiratory Questionnaire		X			X
Chronic Respiratory Questionnaire		X	X	X	X
Baseline Dyspnea Index Questionnaire		X	X	X	X
Medication review		X	X	X	X
Fagerstrom Questionnaire		X			
Tobacco Interview Form		X			
Six Minute Walk Test w/BORG Scale		X			X
Vitals		X	X	X	X
Height & weight		X			
Exhaled CO Smokerlyzer		X	X	X	X
Pulmonary Function Tests a		X			X
IV Catheter placement		X			X
Blood draw for serum creatinine		X			X
Blood draw for serum cotinine		X	X	X	X
Blood draw for C-reactive protein level		X			X
Blood draw for serum and plasma		X			X
Urine pregnancy test in WOCBP		X	X	X	X
Urine sample for bio specimen collection		X			X
Contrast perfused blood volume (PVC) CT scan b		X			X
Non-contrast CT scan		X	X	X	X
Smoking cessation enrollment		X			
Smoking cessation in person follow-up**			X	X	X
Review and record any SAE/AE or medication changes			X	X	X
Dispense medication/placebo		X	X	X	

**\*\*Subject smoking cessation follow-up phone calls will be done once per week by study coordinator while subject is enrolled in the study.**

a. At baseline visit, DLCO will be repeated after 2nd contrast CT scan

b. At baseline visit, two contrast PVC CT scans will be done. One PVC CT will be done pre-dose and one PVC CT will be obtained 60 minutes post-dose.

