### ***CT Scans***

A subject may undergo 13 total low-dose scans throughout the study within 3 months:

**Baseline Visit:** 3 low-dose non-contrast CT volumetric research scans (TLC, FRC, RV) and 2 low-dose dual-energy contrast CT research scans at FRC.

**30-day Visit:** 2 low-dose non-contrast CT Volumetric research scans (TLC, RV)

**60-day Visit:** 2 low-dose non-contrast CT Volumetric research scans (TLC, RV)

**90-day Visit:** 3 low-dose non-contrast CT Volumetric research scans (TLC, FRC, RV) and 1 low-dose dual-energy contrast CT research scan at FRC.

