### ***Smoking Cessation***

Subjects will enter a 3-month smoking cessation program overseen by [name] and [name] who run the hospital-based smoking cessation program. [name] study coordinator will work full time in cooperation with the University of Iowa Hospitals and Clinics Smoking Cessation Clinic in the Pulmonary Rehabilitation Program to maximize success rate. The clinic operates under the Surgeon General's Clinical Practice Guideline Treating Tobacco Use and Dependence: 2008 Update. The study team will meet with the subject in person at the baseline, 30 day, 60 day and 90 day visits and follow up by phone weekly. At the baseline visit the subject will be asked to taper down their use of tobacco for the first week in the study prior to their commitment to quit smoking for the remainder of the study.

Follow up will seek to identify problems already encountered and potential challenges in the immediate future, assessment of current medication use and problems, and restatement of resources to help support them during their tobacco use cessation such as quit-line support.

If tobacco use has occurred, a review of the circumstances and encouragement to recommit to total abstinence will be done.

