Image Quantitation and Outcome Measures: Lung density histogram-based measures of parenchymal characteristics and PBV parameters extracted using the Siemens software for material decomposition will serve as the primary metrics in this project. Regional PBV will be expressed as a percent of the total lung PBV. The primary outcome measure in this study will be CV of PBV and regional ventilation along with neutrophil accumulation assessed by SPECT. The primary measure used to assess lung parenchyma in the non-contrast scans will be the percent of lung falling below -950 HU. Secondary measures include the position of the lower 15th percentile point on the lung density histogram (P15) and “Alpha” negative of the slope of the log-log plot of the number of holes plotted against hole size (44) with holes defined as connected voxels < -950 HU. In all of the volume scans we will extract the lungs, lobes, sub-lobe segments, airway tree out to two generations beyond the segmental airways as outlined in (1) in addition to assessing CV of PBV and ventilation (from image matching) and lung density measures for completeness of lung characterization. From the image matching, we will have lung density on a region-by-region basis at an acinar level of detail. Based upon density changes within a known regional volume of lung, we have a measure of regional ventilation. In the Sildenafil study, change in DLCO (pre and post Sildenafil) will serve as a secondary outcome measure with the expectation that as inflamed lung regions are perfused, DLCO will drop but that this will recover in the smoking cessation follow-up and will correlate with a drop in total lung density on the TLC scans. In addition to evaluating CV of PBV and ventilation, we will warp pre and post hypoxia and Sildenafil PBV image sets and test whether the regions of highest PBV remain high under hypoxia in the emphysema susceptible smokers and whether the regions of low PBV increase with Sildenafil. This test will significantly strengthen the link back to our primary hypothesis. Image matching software developed in house (53, 55-59) will be used to correlate data from the non-contrast volume scan and the PBV DECT scan. Heterogeneity of PBV will be assessed using our in-house PASS software. All other analysis will be assessed via VIDA’s (Software derived from our laboratory and now commercialized and FDA 510K cleared) Apollo software. The VIDA software together with PASS has analyzed over 50,000 CT data sets from a growing number of multi-center investigations. Details of analysis approaches are given in (1). Segmentation results are passed between Apollo and PASS. In PASS, we are able to use the vascular tree extracted by Apollo to identify the vascular paths that serve to define the sub-lobe segments. We will use these lobar and sub-lobe demarcations as the basis for evaluating PBV heterogeneity and lung density metrics in the emphysema susceptible and emphysema-free normal smokers.

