
Statistical Analysis

For outcome variables that meet a normal distribution error assumption (or are suitable to normalization through a transformation) our statistical analysis for Aims 1-4 will be primarily based on general linear models with identity link and normality of errors. Specifically, we will look at increasing/decreasing trends of the outcome variable as well as pair-wise comparisons across groups. These pair-wise comparisons will be obtained as orthogonal contrasts within the linear models. For those variables that do not meet the assumptions of the general linear models

we will use generalized additive models (GAM). These regression models allow for exploration of nonparametric relationships of an outcome variable with a number of independent variables simultaneously and identify associations when the response variable is not normally distributed or equal variance assumptions are not met. PBV measures will also be assessed using Bland-Altman methods, with adjustment for heteroscedasticity if present. For comparisons that involve an intervention (e.g., hypoxia and Sildenafil), differences between study groups will be estimated by a time (pre/post)*group interaction term in linear models with generalized estimating equations.

All models will be adjusted for covariates. Covariates will be considered for inclusion into regression models based principally on plausible evidence and secondarily on evaluation of statistical associations in the dataset. Data from multiple scans of the lung of a subject are generally spatially and/or temporally correlated; we will account for such correlation in the analysis, e.g. as random effects in a linear mixed model (113) Since a major interest in this study is to investigate differences between ordinal groups we perform pair wise comparisons between groups. To control the experiment-wise type I error (“multiple comparisons”), we use the Holm step-down procedure, an improved version of the Bonferroni criterion. Subject dropout and resultant missing data in the smoking cessation project will use the Generalized Estimating Equation GEE to impute the missing values for our generalized linear model analysis of the data.

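### If the SAP's pre/post-by-group interaction is used for sildenafil against placebo, it does not say which of two post-dose PBV scans counts, and it is usually less precise than a baseline-adjusted arm contrast

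*SAP*

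**What the plan says.** **Estimator.** The SAP's Statistical Analysis section has one estimator that names sildenafil. For interventions, with hypoxia and sildenafil as its examples, "differences between study groups will be estimated by a time (pre/post)*group interaction term in linear models with generalized estimating equations". Time has two levels there, and the study groups are not defined.

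**Scope.** The section begins from "our statistical analysis for Aims 1-4 will be primarily based on general linear models with identity link and normality of errors". The Protocol (Overview) puts the randomised trial under another aim: "For Aim 5 80 (ages 25-65) Gold 0-2 subjects that are current smokers". The section's last sentence does reach the cessation setting: "Subject dropout and resultant missing data in the smoking cessation project will use the Generalized Estimating Equation GEE".

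**Outcome.** The SAP (Image Quantitation and Outcome Measures) states: "The primary outcome measure in this study will be CV of PBV and regional ventilation along with neutrophil accumulation assessed by SPECT". No time point is attached.

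**Timing.** Note b to the Protocol's schedule covers the baseline visit: "One PVC CT will be done pre-dose and one PVC CT will be obtained 60 minutes post-dose". PVC there is the perfused-blood-volume scan, called PBV in the SAP. The CT Scans section adds at day 90 "1 low-dose dual-energy contrast CT research scan at FRC". At the baseline visit subjects are only "asked to taper down their use of tobacco for the first week in the study prior to their commitment to quit smoking" (Smoking Cessation), so the two post-dose scans fall on either side of the quit commitment.

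**Covariates and multiplicity.** The SAP promises covariate adjustment in every model without naming the pre-dose value. It ties the Holm procedure to pair-wise comparisons between groups.

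**The concern.** Two questions arise if this interaction is used for the randomised comparison.

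The first is which scan is *post*. At 60 minutes the scan shows an acute response before cessation has begun. At day 90 it comes after the treatment period and the quit attempt. These are different estimands. With a two-level factor and no named time, either scan would satisfy the text, so the choice could be made once results are known, for part of the primary outcome.

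The second is whether change from baseline is the best use of the pre-dose scan. Under randomisation the arms have the same expected baseline. Weighting the baseline by its regression slope, rather than by 1, then normally gives a smaller variance. With at most 40 subjects per arm that is worth having.

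**Working it through.** **Inputs.** From the Protocol: 80 subjects (Overview) in equal numbers (Randomization), so n = 40 per arm. The available text gives no alpha, power, SD, dropout rate or pre/post correlation, so the figure of 80 cannot be reproduced. Assumed here: two-sided 5%, 80% power, SD 1 at every scan, the same correlation ρ between any two of the three scans, and complete data.

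**1. Scan count.** All scans: 5 + 2 + 2 + 4 = 13. Contrast scans: 2 + 1 = 3. Both agree with the Protocol (CT Scans; Exposure Output). One contrast scan is pre-dose, so two are post-dose.

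**2. Choosing between the two post-dose scans.** The correlation between the two arm contrasts is:
- change scores: (1 − ρ) / [2(1 − ρ)] = 0.5;
- ANCOVA: (ρ − ρ²) / (1 − ρ²) = ρ/(1 + ρ) = 0.23, 0.33, 0.41, 0.47 for ρ = 0.3, 0.5, 0.7, 0.9.

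The chance under the null that at least one |z| exceeds 1.96 (bivariate normal) is 9.1% for change scores and 9.6%, 9.5%, 9.3%, 9.2% for ANCOVA. For contrast correlations from 0.9 down to 0 it runs from 7.0% to 9.75% (the last is 1 − 0.95²). This treats both times as randomised contrasts.

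**3. Precision.** With a group main effect, two times and complete data, the interaction equals the difference between arms in mean change.
- Interaction variance: 4(1 − ρ)/n.
- ANCOVA variance: 2(1 − ρ²)/n in large samples. Estimating the slope multiplies this by 1 + 1/(2n − 4) = 77/76 = 1.013.
- Large-sample ratio: (1 + ρ)/2.
- Detectable difference: (1.96 + 0.84) × √variance, in SD, without the slope cost.

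| ρ | Interaction variance | ANCOVA variance | Ratio | Ratio with slope cost | Detectable, interaction | Detectable, ANCOVA |
|---|---|---|---|---|---|---|
| 0.3 | 0.0700 | 0.0455 | 0.65 | 0.66 | 0.74 | 0.60 |
| 0.5 | 0.0500 | 0.0375 | 0.75 | 0.76 | 0.63 | 0.54 |
| 0.7 | 0.0300 | 0.0255 | 0.85 | 0.86 | 0.49 | 0.45 |
| 0.9 | 0.0100 | 0.0095 | 0.95 | 0.96 | 0.28 | 0.27 |

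Simulation (20,000 trials per ρ, 40 per arm) gave ratios of 0.66, 0.76, 0.86 and 0.96. The gain is zero where (1 + ρ)/2 × 77/76 = 1, that is ρ = 2 × 76/77 − 1 = 0.974. With 32 per arm (20% loss, assumed) the factor is 61/60 and ρ = 2 × 60/61 − 1 = 0.967.

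**4. Whether general covariate adjustment supplies the gain.** An additive baseline term takes the same value at both times for a subject, so it cancels from the change. In one simulated data set the GEE interaction and the difference in mean change were both 0.3812. Adding age or the pre-dose value as a main effect left the estimate and its standard error (0.1596) unchanged. ANCOVA on the same data had a standard error of 0.1517. A baseline-by-time term does reproduce the ANCOVA estimate, because it frees the slope at the post-dose time.

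**The case against.** **The two-level factor may fit what it was written for.** The section opens with Aims 1-4, and the sentence pairs sildenafil with hypoxia, which is not in this Protocol's schedule. The SAP's outcome section describes matched pre and post PBV images for both challenges, and it separates DLCO change around sildenafil from recovery during cessation follow-up. Notes a and b to the schedule fit an acute pre/60-minute pair. This stands as a reading. On it, however, the available text has no estimator for the randomised day-90 comparison, so clarification is still needed. The opening part of the SAP was not available to this review, and an estimator or primary time there cannot be excluded.

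**Repeated scans and multiplicity were foreseen.** The SAP expects temporal correlation, suggests random effects, and brings in Holm for experiment-wise error. True, but none of this names a time, and Holm is attached to group comparisons. If Holm were stated to cover both times, the 9% would not arise.

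**The covariate form is open.** A baseline-by-time term is not excluded. This stands: the gain is unspecified, not ruled out.

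Three stronger readings are tempting, and the documents do not support them:
- *The estimator is biased.* It is unbiased under randomisation.
- *Adjustment is a free gain.* The interaction already uses the pre-dose value, adjustment costs one slope (about 1.3% of variance), and ρ is not given.
- *Both post-dose scans will be averaged, with a heavy loss of power.* No section proposes averaging, and the size rests on assumed correlations. If the effect is at one time only, 80% power becomes 37% with equal correlations. With 0.9 between the two baseline-visit scans and 0.6 between each and day 90, it becomes 21% (effect at 60 minutes only) or 63% (day 90 only). With equal correlations and equal effects at both times, power rises to 90%.

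**Conclusion.** The point holds conditionally: if the interaction is meant for the Aim 5 randomised comparison, it should be revised.

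The main gap is that *post* is undefined for part of the primary outcome. A choice made after the data are seen would give a false-positive rate of about 9% instead of 5% (7.0% to 9.75% over the range of contrast correlations shown), unless Holm is stated to cover both times.

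The second part is an improvement, not the correction of an error. Baseline adjustment lowers the variance by about 35%, 25%, 15% or 5% at assumed correlations of 0.3, 0.5, 0.7 or 0.9, about one percentage point less after the slope cost. It gains nothing above about 0.97. These figures assume equal SDs, complete data and 40 per arm.

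Confidence is medium, because the scope of the sentence is uncertain and part of the SAP was not available.

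**What to change.** For the randomised comparison, the SAP should:

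1. Say whether the sentence applies to Aim 5 and, if so, define *group* as the randomised arm.
2. Use three time levels for PBV: pre-dose, 60 minutes and day 90. The sponsor names the primary time for each outcome, including DLCO, before data are seen. The other time is reported as a separate contrast, or Holm is stated to cover both.
3. Estimate the arm effect at each post-dose time by ANCOVA on the pre-dose value. Equivalent routes are a baseline-by-time term in the same model, or baseline means constrained equal across arms.
4. Keep the unconstrained interaction for hypoxia and other non-randomised comparisons, where equal baseline means cannot be assumed.

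The Protocol's schedule and its Randomization section must also be reconciled on whether the dose before the 60-minute scan is the randomised product. Report a between-arm contrast at 60 minutes only if it is; otherwise label that result a within-subject change.

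The cost is wording, one estimated slope per contrast, and two decisions by the sponsor: the primary time for each outcome, and a statement of what the 60-minute dose is. No extra scan or subject is needed.

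### The two-level pre/post term does not say which visits are post, so the 30- and 60-day lung density values have no stated place in the sildenafil-placebo comparison

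*SAP*

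**What the plan says.** **Scans.** In the protocol (CT Scans), baseline has "3 low-dose non-contrast CT volumetric research scans (TLC, FRC, RV) and 2 low-dose dual-energy contrast CT research scans at FRC". The 30- and 60-day visits each have "2 low-dose non-contrast CT Volumetric research scans (TLC, RV", with no FRC and no contrast scan. Day 90 has "3 low-dose non-contrast CT Volumetric research scans (TLC, FRC, RV) and 1 low-dose dual-energy contrast CT research scan at FRC".

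**Outcomes.** The SAP (Image Quantitation and Outcome Measures) states: "The primary outcome measure in this study will be CV of PBV and regional ventilation", together with a SPECT measure. The percent of lung below -950 HU is the primary parenchymal measure on the non-contrast scans.

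**Analysis.** The SAP (Statistical Analysis) ties its general linear models to Aims 1-4, whereas the protocol Overview calls this trial Aim 5. For comparisons involving an intervention, with hypoxia and sildenafil as its examples, it says group differences will be "estimated by a time (pre/post)*group interaction term in linear models with generalized estimating equations". Two further sentences matter. On repeated scans: "Data from multiple scans of the lung of a subject are generally spatially and/or temporally correlated; we will account for such correlation in the analysis", with random effects in a linear mixed model as the example. On dropout: "Subject dropout and resultant missing data in the smoking cessation project will use the Generalized Estimating Equation GEE to impute the missing values". The supplied text does not map post to a visit or mention the 30- or 60-day visits in the analysis.

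**The concern.** Density exists at four visits, but the only arm-comparison term that names sildenafil distinguishes two times. Each reading of post has a cost.

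- **Post is day 90.** A subject who leaves after day 30 or day 60 has follow-up density values that do not inform the arm contrast. Unweighted GEE then generally needs dropout to be completely at random. Calling GEE a way to impute does not change this, because GEE is an estimator and not an imputation method.
- **Post is every follow-up visit.** The estimate is an average over 30-90 days that nobody has labelled as such.

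Unless the choice is written down, it can be made after the data are seen. The plan expects dropout in a cessation study and already collects the values that could help correct for it.

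**Working it through.** **Plan's own figure.** Baseline 3+2 = 5, day 30 = 2, day 60 = 2, day 90 3+1 = 4; the total is 13, as the protocol states. Four of the 10 non-contrast scans fall at days 30 and 60.

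**Inputs.** 80 subjects (protocol Overview) in equal numbers (Randomization), so 40 per arm. The supplied text gives no within-subject correlation, dropout rate, alpha or effect size. Assumed here: SD 1 at each visit; compound-symmetric (CS) or AR(1) correlation of 0.5, 0.7 or 0.9; 0-40% dropout by day 90 in equal steps; two-sided 0.05 and 80% power.

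**1. Day-90 precision, complete data.** Variance of the arm difference in change = 2 x 2(1-rho)/40. At CS 0.7 this is 0.030, SE 0.173, with or without the interim visits. The variance ratio (four visits over two) was 1.000 at every correlation tried.

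**2. Day-90 precision, completely-random dropout.** Example: CS 0.7, with 36, 32 and 28 of 40 per arm observed at days 30, 60 and 90.
- Two visits: 2 x [(1-0.7^2)/28 + (1-0.7)^2/40] = 2 x [0.01821 + 0.00225] = 0.0409, SE 0.202.
- Four visits, adding the variance from each visit regressed on the earlier ones: 2 x [0.3875/28 + 0.2917^2 x 0.4235/32 + 0.4118^2 x 0.51/36 + 0.3^2/40] = 2 x 0.01962 = 0.0392, SE 0.198.
- Variance ratio 0.959; detectable difference (1.96+0.84) x SE = 0.55 against 0.57 SD.

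Range of the ratio over all correlations:

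| Dropout by day 90 | Variance ratio, four visits / two |
|---|---|
| 20% | 0.94-0.99 |
| 30% | 0.91-0.98 |
| 40% | 0.87-0.97 |

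**3. Bias when dropout depends on interim change.** 2,000 simulated trials per setting; active-arm means 0, 0.17, 0.33, 0.50 SD and placebo means 0. The log-odds of leaving after day 30 or day 60 was -2 in the placebo arm and -2 + 1.5 x (change so far) in the active arm. Both analyses used generalised least squares with the true covariance, so they differ only in the visits included.

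| Correlation | Dropout, placebo/active | Two visits | Four visits |
|---|---|---|---|
| CS 0.7 | 22% / 37% | 0.391 | 0.497 |
| AR(1) 0.7 | 23% / 38% | 0.318 | 0.509 |
| AR(1) 0.9 | 22% / 34% | 0.379 | 0.497 |

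The two-visit shortfall is 0.50-0.391 = 0.11 to 0.50-0.318 = 0.18 SD. The largest Monte Carlo standard error is 0.280/sqrt(2000) = 0.006.

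**4. Pooled post.** If the effect builds linearly to day 90, the average is (1/3 + 2/3 + 1)/3 = 2/3 of the day-90 effect. If the effect is equal at each visit, pooling gives a real precision gain. The baseline-adjusted variance is proportional to (1+2rho)/3 - rho^2 for the mean and 1 - rho^2 for day 90. The SE ratio is sqrt(0.4167/0.75) = 0.745 at rho 0.5 and sqrt(0.1233/0.19) = 0.806 at rho 0.9. Under a linear build that gain is more than lost: effect over SE, relative to day 90, is 0.667/0.745 = 0.89 to 0.667/0.806 = 0.83.

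**The case against.** **The interim scans are not excluded.** A reader might infer from the two-level term that the 30- and 60-day scans have no role. The documents do not say so. Post is undefined and could cover all follow-up. The SAP separately promises to model temporal correlation and addresses dropout, and part of it was not available for this review. This stands: the role is unspecified. But the correlation sentence adds no time levels and names no target contrast.

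**The term may describe the acute challenge.** Sildenafil is paired with hypoxia, and the protocol takes a contrast scan before and 60 minutes after dosing at baseline. If that is the meaning, the supplied text names no term for the 90-day arm comparison, and the need to state one is greater.

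**Precision.** A reader might infer that leaving out interim scans costs substantial precision. For the day-90 contrast it costs none with complete data and little under random dropout. The 19-25% lower SE in step 4 belongs to the 30-90 day mean under an equal effect at each visit.

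**Primary outcome.** A reader might take the whole primary outcome to be affected. CV of PBV has no interim scans. Regional ventilation has them only if it comes from TLC-RV matching; the SAP does not name the volume pair, and FRC is scanned only at baseline and day 90.

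**The bias is constructed.** The mechanism was chosen, it acts in one arm, and it suits a model that uses interim values. This stands as a limit on the size. With no treatment effect and the same mechanism in both arms, the bias would cancel.

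**Conclusion.** The concern holds in limited form. The SAP does not define post or say how the 30- and 60-day density values enter the sildenafil-placebo comparison, and a better method than the stated term is available from data already planned.

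The main stake is robustness to dropout under the day-90 reading. The illustrated bias of 0.11-0.18 SD on a true 0.50 SD effect shows what can happen under an assumed mechanism, with assumed rates and correlations; it does not forecast this trial. Under the pooled reading the stake is interpretation, with 2/3 of the day-90 effect if the build is linear. The day-90 precision gain is small, about 1-13% of variance with 20-40% random dropout.

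The point applies to the density measures and, conditionally, to regional ventilation. It does not apply to PBV or DLCO. A likelihood model also has a limit: it handles dropout explained by observed values, not dropout driven by values never seen.

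**What to change.** For the density measures, and for regional ventilation if TLC-RV matching is used, amend the SAP to:

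- state the lung-volume pair from which regional ventilation is derived;
- replace the pre/post term with visit (30, 60, 90 days) by randomised arm, with the baseline value as covariate;
- fit this as a likelihood-based linear mixed model with unstructured within-subject covariance, in place of the wording about imputing by GEE;
- make the day-90 arm contrast the main result, and report the 30-90 day mean contrast as a labelled secondary result outside the primary Holm family.

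Leave PBV and DLCO unchanged, since they have no 30- or 60-day values.

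The cost is SAP wording only, with no new scans, visits or data. The model carries a few more covariance parameters (3 variances + 3 covariances = 6 for three follow-up visits) and adds one secondary contrast. Unstructured covariance and baseline adjustment go beyond the SAP's random-effects example, so both should be written out explicitly.

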### ***Blood and Urine Collection***

Blood samples will be taken to test the subject's creatinine, cotinine and C-reactive protein level. Two additional tubes of blood will be drawn for serum and plasma collection (baseline and 90 day visit). The creatinine level will only be tested prior to the contrast CT (baseline visit and 90 day visit). The cotinine and C-reactive protein level will be tested at baseline, 30 day, 60 day, and 90 day visits. Women of child bearing potential (WOCBP) will have a urine pregnancy test.

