### ***Randomization***

Subjects will then be randomized to either Sildenafil, 20 mg orally 3x/day, or Placebo in equal numbers after beginning the smoking cessation program above.

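### If baseline covariates enter the sildenafil model only as main effects, the promised adjustment adds no precision to the time-by-group estimate; the SAP should say how they enter

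*SAP*

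**What the plan says.** The Statistical Analysis section of the SAP says that, for comparisons involving an intervention (hypoxia and sildenafil are its examples), "differences between study groups will be estimated by a time (pre/post)*group interaction term in linear models with generalized estimating equations". The next paragraph says "All models will be adjusted for covariates" and gives the selection rule: "Covariates will be considered for inclusion into regression models based principally on plausible evidence and secondarily on evaluation of statistical associations in the dataset". The only product term written anywhere in the section is time by group. The section names no covariate. It does not say whether covariates are baseline or time-varying, or whether they enter as main effects or also multiplied by time. It mentions neither a change-score model nor adjustment for the pre-treatment value. It says that within-subject correlation will be accounted for, with random effects as an example, but fixes neither the working correlation nor the type of standard error for the GEE. It expects incomplete data: "Subject dropout and resultant missing data in the smoking cessation project will use the Generalized Estimating Equation GEE to impute the missing values".

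The Protocol gives the size of the comparison. The Overview plans "For Aim 5 80 (ages 25-65) Gold 0-2 subjects that are current smokers", and the Randomization section allocates sildenafil "or Placebo in equal numbers after beginning the smoking cessation program above", so about 40 per arm.

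**The concern.** The sentence on covariates covers every model, but its effect differs between them. In the cross-sectional group comparisons of Aims 1-4, a main effect for a baseline covariate removes outcome variance and sharpens the contrast. In the pre/post model, the quantity of interest is a difference in change, and a covariate that is constant within a subject contributes nothing to the change. An analyst who follows the text as written would most naturally add baseline covariates as main effects. The report would then describe the randomised comparison as covariate-adjusted when the adjustment had done no work.

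Naming the covariates in advance would not cure this, because a fully pre-specified list entered as main effects cancels in the same way. What is at stake is precision in a trial of about 40 per arm, whose entry criteria span GOLD 0 to 2 and any smoking history above 5 pack-years. A reader could also believe that chance differences in predictors of change had been adjusted for when they had not.

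**Working it through.** **Inputs.** N = 80, equal arms (Protocol, Overview and Randomization). Estimator: time-by-group interaction, linear model, GEE (SAP, Statistical Analysis). The documents give no figure on this point to reproduce, and no R² for change, outcome SD or dropout rate, so all of these are assumptions below.

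**1. Algebra.** Let t = 0 (pre) or 1 (post), g = arm and x = a baseline covariate. With x as a main effect:

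E[Y] = b0 + b1·t + b2·g + b3·t·g + c·x

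Subtracting the pre record from the post record gives E[change] = b1 + b3·g. The term c·x has gone. With both records present, the estimate of b3 is the between-arm difference in mean change, with or without x. Adding d·x·t gives E[change] = b1 + b3·g + d·x, which is a regression of the change on arm and covariate. Only in that form does x act on the contrast.

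**2. Check of the identity.** One simulated trial, 40 per arm, complete pairs:

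| Model | Estimate | Robust SE (GEE) | Random-intercept SE |
|---|---|---|---|
| No covariate | -0.815485 | 0.207185 | 0.209826 |
| x as main effect | -0.815485 | 0.207185 | 0.209825 |

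Independence and exchangeable working correlation gave the same estimates and robust SEs. Over 400 simulated trials (exchangeable), the largest differences were 3e-16 (estimate) and 2e-15 (robust SE).

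**3. Where the identity stops.** Same simulation, 400 replicates, exchangeable GEE, robust SE, each compared with the unadjusted model on the same data:

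| Data | Terms added | Mean (max) shift in estimate | Mean SE ratio |
|---|---|---|---|
| Complete | x | 0 | 1.000 |
| 20% random dropout | x | 0.026 (0.114) | 1.011 |
| About 25% dropout, depending on x and arm | x | 0.111 (0.319) | 1.019 |
| Complete | x and x·t | 0.086 (0.36) | 0.871 |
| 20% random dropout | x and x·t | 0.086 (0.387) | 0.887 |
| About 25% dropout, depending on x and arm | x and x·t | 0.103 (0.407) | 0.912 |
| Complete | x and time-varying smoking | 0.046 (0.199) | 0.971 |

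With dropout, a main effect moves the estimate but does not reduce the SE. A separate simulated data set with 25% of day-90 values missing gave 0.156 unadjusted and 0.155 with main effects. In complete data, the model-based SE under independence does change (0.3137 to 0.2664), but that SE ignores the within-subject correlation that the SAP says it will account for.

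**4. Size of the available gain.** With complete pairs, the change-score regression has 80 - 2 = 78 residual degrees of freedom, and 75 with three covariate parameters. If the covariates explain a share R² of the within-arm variance of change:

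SE ratio ≈ sqrt((1 - R²) × 78/75)

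| Assumed R² | SE ratio | Equivalent sample-size factor (1/ratio²) |
|---|---|---|
| 0.02 | sqrt(0.98 × 1.04) = 1.010 | 0.98 |
| 0.10 | sqrt(0.90 × 1.04) = 0.967 | 1.07 |
| 0.20 | sqrt(0.80 × 1.04) = 0.912 | 1.20 |
| 0.30 | sqrt(0.70 × 1.04) = 0.853 | 1.37 |

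Break-even is R² = 1 - 75/78 = 3.8%. If GOLD class is entered at three levels with sex and pack-years, there are four parameters and break-even is 1 - 74/78 = 5.1%.

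Single data sets scatter widely around such averages. Adding products with time changed the robust SE from 0.1473 to 0.1271 (14% lower) in one, from 0.1448 to 0.1415 (2% lower) in another, and from 0.2072 to 0.2156 (4% higher) in the trial of step 2. These data sets used different assumed covariate effects.

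**The case against.** A reader might infer that covariate adjustment cannot change the sildenafil result at all, or that the comparison is left biased. The documents support neither.

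- **Main effects are not stated.** The SAP is silent on form; it does not exclude products with time. Main-effects-only is the natural reading of a section whose only written product is time by group, but it is a reading. This stands, so the point has to be conditional.
- **Time-varying covariates do not cancel.** The Protocol says "The cotinine and C-reactive protein level will be tested at baseline, 30 day, 60 day, and 90 day visits" (its schedule table lists C-reactive protein only at baseline and day 90), and smoking exposure is an obvious candidate in a cessation trial. This stands against any claim of impossibility. It does not fill the gap, because the SAP names no such covariate, and values taken after treatment starts are not a baseline adjustment.
- **Incomplete pairs are expected.** With dropout, even a baseline main effect moves the estimate, as step 3 shows. This stands for the estimate. It does not show a gain in precision. The cancellation is closest to exact for the pre-dose and 60-minute post-dose contrast scans, both taken at the baseline visit, and least secure at 90 days.
- **No validity problem is shown.** Under randomisation, chance imbalance does not bias the difference in change, and the unadjusted SE already allows for it. This stands fully: the issue is efficiency and accurate description.
- **The gain is assumed.** No document says how much of the change in the outcomes these covariates explain, and for weak covariates the product terms cost slightly more than they return. This stands, which is why the gain is given as a range that includes a loss.

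**Conclusion.** The point holds in conditional form. Baseline covariates entered only as main effects leave the time-by-group estimate and its robust or random-intercept SE as they were, among subjects with both records. That part is algebra and needs no assumption about effect sizes. With dropout the estimate can shift, by amounts that depend on the dropout mechanism, without a material improvement in SE.

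The consequence is forgone precision: about 3%, 9% or 15% of the SE for an assumed R² of 0.10, 0.20 or 0.30 with three covariate parameters, and a slight loss below about 4%. Those sizes rest on assumed R² values and complete pairs. It is more than missing detail, because a complete list of covariates would still do nothing for this contrast unless their form is also set. It does not threaten the validity of the randomised comparison.

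**What to change.** In the Statistical Analysis section, add one sentence for intervention comparisons, along these lines: *Each of two or three baseline covariates named here enters the model together with its product with time; equivalently, they enter a regression of the change score on study group.* Main-effect adjustment can stay for the cross-sectional models of Aims 1-4.

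A model of the post value is an alternative only if it also includes the pre value. Without it, the model is not equivalent and can be less precise than no adjustment: in one simulated data set the post-value model had an SE of 0.200, against 0.145 for the unadjusted interaction. With the pre value included and equal SDs at both times, the SE relative to the change score is sqrt((1 + rho)/2), which is 0.806, 0.866, 0.922 and 0.949 for an assumed pre/post correlation rho of 0.3, 0.5, 0.7 and 0.8.

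The cost is one sentence and about 3 of 78 degrees of freedom, or 4 if three-level GOLD class is used with sex and pack-years. Because weak covariates bring a small net loss, the list should be short and limited to variables expected to predict change. The data needed are already collected at baseline.
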